Endogenous CS is characterised by chronic hypercortisolism, resulting in metabolic dysregulation and comorbidities. Manifestations may be overt or subtle depending on severity of hypercortisolism. Comorbidities include menstrual irregularities and hirsutism in women, dermatological problems with striae, bruising, atrophy, hyperpigmentation, and fungal infections, obesity with moon facies, enlarged supraclavicular fat pads, and dorsal fat pad, glucose intolerance and diabetes, sleep apnoea, cardiovascular disease, venous thromboembolic events, bone loss, neuropsychiatric disease, and potentially severe infections. Whereas untreated Cushing's syndrome had a 50% five-year mortality rate, treatment to control cortisol production should substantially mitigate the risk of death due to hypercortisolism (Nieman et al. 2015).

Endogenous CS is a rare disease. Estimates of regional incidence have been limited and vary by aetiology and possibly methodology. CD is the most common cause of endogenous CS, with an estimated incidence in Europe of up to 2.4 per million and in the US of up to 7.6 per million depending on the series (Etxabe and Vazquez 1994; Broder et al. 2015; Tabarin et al. 2022). Adrenal tumours represent ~20% of CS cases (but may be higher in some countries such as Japan (Tanaka et al. 2020) and Italy (Invitti et al. 1999). Ectopic ACTH secretion from neuroendocrine tumours represent 10-15% of known CS cases. Different diseases causing CS manifest at different ages, i.e., smoking-related non-small lung cancer increases after the age of 50 years, neuroendocrine (carcinoid) tumours

Final v2.0 26 of 63 18 April 2023

occur earlier in adulthood, and adrenal tumours have bimodal age peaks (1st decade and 40-50 years old), whereas the peak incidence for CD is in women 25-45 years old (Bertagna and Orth 1981; Luton et al. 1990). CD occurs approximately 3 times than in men, women have a 4-5 times greater incidence of adrenal tumour causing CS, and neuroendocrine tumours causing CS are similar in incidence between the sexes (Carpenter 1988; Nieman et al. 2015). Heterogeneity in the cause and populations affected by non-CS CS, support the need of a dedicated efficacy and safety study focusing on non-CD CS population. Patients with CS have increased mortality, which applies both to patients with pituitary-dependent CS and adrenal-dependent CS, as well as patients with ectopic CS who have the worst prognosis (Ragnarsson et al. 2019).

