#### Type of non-CD Cushing Syndrome

- 1) ACTH-dependent CS: Patients classified as "Ectopic Adrenocorticotropic Hormone Secretion" in the "CS Disease Causation".
- 2) Adrenal CS: Patients with "Adrenal Adenoma", "Adrenocortical Carcinoma" in the "CS Disease Causation".
- 3) Unclassified: "Adrenal hyperplasia" and "Other" in the "CS Disease Causation".

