#### 5.3.6 Stratified Analysis

Project Document Version No.: 4.0; Document Effective Date: 30 October 2023

CONFIDENTIAL

RECORDATI AG, Rare Diseases Branch LCI699-RECAG-NI-0596

Statistical Analysis Plan

For the potential confounding identification objective, participants will be stratified if they received or did not receive other therapies for Cushing's syndrome (regardless of the type of therapy) from start of study treatment to week 12. The statistical null hypothesis states that the response rates at the end of the 12-week period (i.e., at Week 12) are the same between the participants with/without non-study CS treatment. To test this hypothesis, a Cochran-Mantel-Haenszel (CMH) exact test by non-study CS treatment (yes/no) will be performed using the ITT.

If the 2-sided p-value is  $\leq$  0.05, and the odds ratio (non-study CS medication treatment yes vs. no) is > 1, the null hypothesis will be rejected and the response rate at week 12 in the non-study CS treatment yes group will be considered higher than that in the non-study CS medication treatment no group.

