# 5.12 Determination of Sample Size

There is no statistical hypothesis testing for this study; therefore, the sample size is not based on formal statistical considerations and, instead, is based on practical considerations.

Historical data will be collected from approximately 100 participants with a diagnosis of non-CD CS with an aetiology of adrenal adenoma, adrenocortical carcinoma, adrenal hyperplasia, or ectopic adrenocorticotropic hormone secretion treated with osilodrostat as follows:

- a) Under the April 2019 French ATU (5th Apr 2019) or
- b) Under conditions of routine clinical practice after commercialization of osilodrostat in France since June 2020.

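### The exact CMH test in SAP 5.3.6 names no stratum, so it is a crude 2×2 test and cannot separate the effect of other Cushing therapy from the type of patient who received it

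*SAP*

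**What the plan says.** SAP 5.3.6 states its aim and its grouping together: "For the potential confounding identification objective, participants will be stratified if they received or did not receive other therapies for Cushing's syndrome", counted from start of treatment to week 12. The null hypothesis is that week-12 response rates "are the same between the participants with/without non-study CS treatment". The method is that "a Cochran-Mantel-Haenszel (CMH) exact test by non-study CS treatment (yes/no) will be performed using the ITT". The decision rule needs a two-sided p-value of at most 0.05 "and the odds ratio (non-study CS medication treatment yes vs. no) is > 1, the null hypothesis will be rejected". No aetiology, site, severity or other control variable appears in the section.

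Aetiology appears elsewhere in the SAP only as a subgroup indicator. SAP 3.5 forms three groups from the recorded cause of disease: ectopic ACTH secretion; adrenal adenoma together with adrenocortical carcinoma; and an unclassified group of adrenal hyperplasia and other causes. SAP 5.10 reports mUFC response by subgroup in the mITT and On-Treatment populations. It does not use the ITT there and does not say that aetiology will be crossed with other therapy. SAP 5.3.5 plans no formal sensitivity analysis, and neither document plans a regression model.

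Protocol 8.7.12 asks for response by receipt of other therapy, with differences in proportions and 95% CIs, and leaves the detail to the SAP.

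**The concern.** A CMH test compares two groups within levels of a third variable and combines the evidence across those levels. Here the only variable named is the one that defines the two groups. If therapy yes/no was instead meant as the stratum, a single-cohort study has no second factor left to compare and the test is undefined. The wording needs correction on either reading.

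Other therapy was not randomised. A crude comparison mixes its effect with differences between the patients who did and did not receive it. The amendment rationale in protocol section 5 says that this analysis was added because other therapies may confound the safety and efficacy results, and the study is meant to support an sNDA. A test that cannot make the separation does not serve that purpose.

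**Working it through.** **Inputs from the documents.** Test, null hypothesis and decision rule: SAP 5.3.6. Sample size: about 100 (SAP 5.12). The documents state no power or expected count for this test, so there is no planned figure to reproduce. They give no rate of other therapy or of week-12 response by aetiology. Every count and rate below is therefore an assumption.

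**Step 1: the one-stratum identity.** With one stratum, CMH chi-square = Pearson chi-square × (N−1)/N, and the exact conditional p is Fisher's p. Check on 25/40 against 30/60: CMH chi-square 1.500, Pearson × 99/100 = 1.500; exact CMH p = 0.3050, Fisher p = 0.3050.

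**Step 2: a masked effect (assumed counts, N = 100).**

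| Stratum | Responders, other therapy | Responders, none | Odds ratio |
|---|---|---|---|
| ACTH-dependent (45) | 12/30 | 2/15 | (12×13)/(18×2) = 4.33 |
| Adrenal (55) | 9/10 | 30/45 | (9×15)/(1×30) = 4.50 |
| Crude (100) | 21/40 (52.5%) | 32/60 (53.3%) | (21×28)/(19×32) = 0.97 |

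- Crude: Fisher p = 1.0.
- Mantel-Haenszel OR = Σ(ad/n) / Σ(bc/n) = (156/45 + 135/55) / (36/45 + 30/55) = 5.921/1.345 = 4.40.
- CMH: observed 21; expected 30×14/45 + 10×39/55 = 9.333 + 7.091 = 16.424; variance 2.192 + 1.719 = 3.911. Chi-square = (21 − 16.424)²/3.911 = 5.35, p = 0.021. Exact conditional p = 0.023.
- 95% CI for the common odds ratio: 1.18 to 16.4 (asymptotic); 1.1 to 24.7 (exact, inverting the conditional distribution of the 21 responders given both strata's margins).

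**Step 3: a false effect (assumed counts, N = 100).** Poorer-response stratum: 3/12 with other therapy, 9/36 without, OR = (3×27)/(9×9) = 1. Better-response stratum: 30/40 and 9/12, OR = (30×3)/(10×9) = 1. Crude: 33/52 against 18/48, OR = (33×30)/(19×18) = 2.89, Fisher p = 0.016. The SAP rule would reject. The Mantel-Haenszel OR is 1.0.

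**Step 4: how often the SAP rule fires.** Two strata of 50, untreated response 25% and 75%, 3,000 simulated data sets per row. The rule is an exact p of at most 0.05 with OR > 1.

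| Within-stratum OR | Share on other therapy (25% stratum / 75% stratum) | Crude | Stratified |
|---|---|---|---|
| 4 | 80% / 20% | 0.8% | 56% |
| 4 | 70% / 30% | 7% | 71% |
| 4 | 60% / 40% | 31% | 78% |
| 4 | 50% / 50% | 69% | 77% |
| 1 | 30% / 70% | 46% | 3% |
| 1 | 20% / 80% | 85% | 2% |

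With untreated response of 40% and 70%, the OR 4 rows become 20% against 59%, 37% against 75%, 59% against 81%, and 78% against 80%; the OR 1 rows become 16% against 2% and 38% against 2%. When other therapy is unrelated to aetiology (50%/50%), crude and stratified results are close.

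**The case against.** The strongest objection is that the documents do not show aetiology to be a confounder here, and that stands. A reader might infer that added therapy goes to the sicker or malignant cases, so that the crude test will hide a real effect. No section gives therapy use or response by aetiology. The protocol background does refer to "patients with ectopic CS who have the worst prognosis", but that sentence is about mortality, not mUFC at week 12. The only evidence in the documents on cause and cortisol is the nine-patient Japanese phase II study, which the background reports as showing lower mUFC in every patient whatever the cause. That concerns reduction rather than normalisation and is very small, but it does not point towards an aetiology effect. The one cortisol-lowering drug that the background ties to a single non-CD cause is mitotane, for adrenal cancer, which SAP 3.5 places in the adrenal group.

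There are nevertheless plausible routes to confounding. Treatment can depend on cause, as with mitotane. Discontinuation before week 12 counts as non-response in SAP 5.3.2, so poor prognosis can lower the response rate. This supports planning for confounding; it does not settle its size or direction.

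A reader might also infer that a null result would lead the response to be credited to osilodrostat. SAP 5.3.6 sets no such rule. It defines only the conclusion for p ≤ 0.05 with an odds ratio above 1.

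It is also fair to say that the subgroup tables by intervention type and by aetiology will make some imbalance visible, and that protocol 8.7.12 does not ask for adjustment. But those tables are not stated to be crossed and do not use the ITT, so they cannot replace a stratified estimate.

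**Conclusion.** The concern holds as a defect of specification. As written, the test is Fisher's exact test on a crude table, in a section whose stated aim is to identify confounding, and no adjusted or crossed ITT analysis elsewhere fills the gap. This follows from the text and needs no assumption.

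The size of any error does rest on assumptions. If aetiology is linked to both other therapy and response, the crude odds ratio can be 0.97 when the within-aetiology value is 4.4, or 2.9 when it is 1. If either link is absent, the loss is small. Masking is therefore one possibility and false detection is another; the documents support neither as a prediction.

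This is a secondary analysis, and the primary estimate is unaffected. The change is worth making because it is cheap and reduces a bias that the section exists to examine. It will not remove confounding. The SAP 3.5 groups pool adenoma with carcinoma, severity is not addressed, and stratified power for an odds ratio of 4 was only 56% to 81% in the masking and balanced scenarios.

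**What to change.** In SAP 5.3.6:

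- Name CS aetiology as the CMH stratum, with other therapy yes/no as the compared factor and week-12 response as the outcome. Use the collected disease-causation categories, or the SAP 3.5 groups with adrenocortical carcinoma kept apart from adenoma where counts allow. Set the collapsing rule before database lock.
- Report the Mantel-Haenszel odds ratio with exact 95% CI, the crude odds ratio beside it, and the difference in proportions with 95% CI from protocol 8.7.12, which SAP 5.3.6 does not carry over.
- State that strata are small, that the interval will be wide, that confounding by severity may remain, and that a non-significant result does not show absence of confounding.

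The cost is a few sentences and one extra table, with no new data. The exact method protects the error rate in sparse strata but does not restore precision.

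Two related points in the same section can be settled in the same edit: the rule is silent on an odds ratio below 1, and a null hypothesis with a rejection rule conflicts with the statements in protocol 8.7.1 and SAP section 3 that no hypothesis will be formally tested.

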8.7 Data Analysis

Statistical analysis of this study will be the responsibility of the sponsor's designee.

Any change to the data analysis methods described in the protocol will require an amendment only if it changes a principal feature of the protocol. Any other change to the data analysis methods described in the protocol, and justification for making the change, will be described in the final statistical analysis plan (SAP). The SAP will be developed as a separate document and approved prior to database lock, containing a description of the planned statistical analysis in detail with Tables, Figures and Listings (TFLs) templates.

Any deviations from the planned analyses will be described and justified in the final study report.

The overview of statistical analysis is detailed in the below section.

Final v2.0 47 of 63 18 April 2023

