8.7.1 Statistical Hypothesis

The study plans to summarize only descriptive outputs and there is no inferential endpoint associated with the study. Hence no formal statistical hypothesis will be tested for this study.

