8.7.2 General Considerations

An SAP describing the planned statistical analysis in detail with TLF templates will be developed as a separate document. All statistical analyses will be performed using Statistical Analysis System® (version 9.4 or higher) unless otherwise stated.

No formal statistical hypothesis testing will be performed, and all the analyses will be primarily descriptive in nature. When appropriate, and unless otherwise specified, 95% confidence intervals (CIs) will be displayed.

Descriptive statistics will include the number of available data, number of missing data and the following:

- Mean and associated standard error of mean (SE) standard deviation (SD), minimum, median, maximum, first and third quartiles and 95% CIs for means/medians, minimum (Min), maximum (Max).
- Counts and percentages of each category for categorical variables with 95% CIs.

Percentages will be based on the number of patients in safety or ITT population.

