8.7.12 Stratified Analysis

The number and proportion of patients with mean urinary free cortisol (mUFC) ≤ULN at 12 weeks will be stratified if they received or not other therapies for Cushing's syndrome (regardless of the type of therapy) and will be summarised descriptively along with associated 95% CI. Differences in the proportions and 95% CI of the different groups will be evaluated. Further details will be described in the final SAP.

Final v2.0 52 of 63 18 April 2023

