- d. Osilodrostat initiation dose and up- and/or down-titration regimens (including dates) and reasons for titration will be recorded in the database during the study.
- e. All prior medications taken within 6 months prior to the first dose of Osilodrostat must be collected.
- f. Baseline mean urinary free cortisol data can be collected within 1 month prior to osilodrostat initiation.
- g. Footnote-a is not applicable to the following assessments: prior medications, concomitant medications and mean urinary free cortisol.
- \*End of data collection may be due to earlier of loss-to-follow-up, death, end of retrospective follow-up period or treatment discontinuation.
- \*CBC includes WBC, RBC, Haemoglobin, Haematocrit, MCV, MCH, MCHC, RDW, Platelet Count, MPV and Differential (Absolute and Percent Neutrophils, Lymphocytes, Monocytes, Eosinophils, and Basophils).
- &CMP includes Albumin, Alkaline Phosphatase, ALT, AST, Calcium, Carbon Dioxide, Chloride, Creatinine with GFR Estimated, Glucose, Potassium, Sodium, Total Bilirubin, Total Protein, (Blood) Urea Nitrogen.
- @ For list of CS-specific examination findings, please refer to protocol section 8.3.2.

As this is a descriptive study, the effectiveness and safety endpoints will be summarized descriptively. No formal statistical hypothesis testing will be performed.

Data from an approximately 100 patients meeting the inclusion/exclusion criteria in France will be collected.

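### SAP 5.3.6 draws a conclusion only when the odds ratio exceeds 1 and names no difference in proportions, although protocol 8.7.12 says differences will be evaluated

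*SAP*

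**What the plan says.** Protocol 8.7.12 plans the proportion with mUFC ≤ULN at 12 weeks, split by whether patients received other Cushing's therapy, with 95% CIs. It adds that "Differences in the proportions and 95% CI of the different groups will be evaluated" and leaves further detail to the SAP. The Amendment 1 table gives the reason: patients on other therapies may confound the safety and efficacy results.

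SAP 5.3.6 supplies the detail. It opens "For the potential confounding identification objective" and defines the strata by other therapy received between the start of osilodrostat and Week 12. It states a null of equal Week 12 response and specifies an exact Cochran-Mantel-Haenszel test in the ITT population. If the two-sided p-value is at most 0.05 and the odds ratio (yes versus no) is above 1, the stated conclusion is that "the null hypothesis will be rejected and the response rate at week 12 in the non-study CS treatment yes group will be considered higher". This is its only decision sentence.

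On testing in general:

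- Protocol 8.7.1: "no formal statistical hypothesis will be tested for this study".
- Protocol 8.7.2: "No formal statistical hypothesis testing will be performed, and all the analyses will be primarily descriptive in nature".
- SAP 3: "No formal statistical hypothesis testing will be performed".
- SAP 5.12: "There is no statistical hypothesis testing for this study".

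On departures from the protocol, protocol 8.7 states: "Any other change to the data analysis methods described in the protocol, and justification for making the change, will be described in the final" SAP. SAP 5.13 says only that some related analyses have been added, and lists no change to the stratified analysis.

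**The concern.** The analysis exists to show whether other therapy distorts the reading of the osilodrostat response. That distortion can run either way. Added therapy could raise response; equally, patients who are harder to control could be the ones given more therapy, which would put the odds ratio below 1 (a plausible mechanism, not one the documents state). A rule that speaks in one direction only does not serve a two-sided question.

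A p-value with a reject rule also gives no effect size. With about 100 patients, a non-significant result is compatible with a large difference, and a reader could take it as reassurance that there is no confounding. The difference mentioned in the protocol would guard against that, and SAP 5.3.6 does not name it.

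**Working it through.** **Reading the text.** The table sets the protocol against SAP 5.3.6.

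| Item | Protocol | SAP 5.3.6 |
|---|---|---|
| Per-stratum proportion and 95% CI | Yes (8.7.12) | Not named; SAP 5.2 supplies Clopper-Pearson as the default |
| Difference in proportions | Yes (8.7.12) | Not named |
| CI for the difference | One reading of 8.7.12 | Not named; SAP 5.2 gives no method for a difference |
| Hypothesis test | None (8.7.1, 8.7.2) | Exact CMH test with a reject rule |
| Conclusion if p≤0.05 and OR>1 | – | Response higher with other therapy |
| Conclusion if p≤0.05 and OR<1 | – | None |

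The plan gives no figure for this analysis, so there is nothing to reproduce. What follows shows the consequence of the rule.

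**Inputs.** The total of 100 comes from SAP 5.12 (approximately 100). The splits 20/80, 30/70 and 50/50 (with/without other therapy) and all response rates are assumptions. SAP 5.3.6 names no further stratifying factor, so the exact CMH test is taken as Fisher's two-sided exact test on one 2×2 table.

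**Formulas.** Wilson limits for x/n with p=x/n and z=1.96: [p + z²/2n ± z√(p(1−p)/n + z²/4n²)]/(1 + z²/n). Newcombe limits for d = p1 − p2, with Wilson limits (l1, u1) and (l2, u2):

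- lower = d − √[(p1−l1)² + (u2−p2)²]
- upper = d + √[(u1−p1)² + (p2−l2)²]

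**Case A: 9/30 with versus 42/70 without other therapy.**

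- OR = (9/21)/(42/28) = 0.29; exact p = 0.0085.
- Wilson limits: 0.1666 to 0.4788 and 0.4829 to 0.7067.
- Lower = −0.300 − √(0.1334² + 0.1067²) = −0.300 − 0.171 = −0.471.
- Upper = −0.300 + √(0.1788² + 0.1171²) = −0.300 + 0.214 = −0.086.
- Per-stratum Clopper-Pearson: 14.7–49.4% and 47.6–71.5%.

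The difference is clearly below 0, yet the rule states no conclusion. The two per-stratum intervals overlap, so they do not show the difference either.

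**Case B: 21/30 versus 35/70.**

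- OR = (21/9)/(35/35) = 2.33; exact p = 0.080, so no rejection.
- Wilson limits: 0.5212 to 0.8334 and 0.3860 to 0.6140.
- Lower = 0.200 − √(0.1788² + 0.1140²) = −0.012.
- Upper = 0.200 + √(0.1334² + 0.1140²) = 0.375.

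Non-rejection here is compatible with a difference of up to about 38 points.

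**Range over splits, observed rates fixed.**

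| Split | 30% vs 60%: p | CI (points) | 70% vs 50%: p | CI (points) |
|---|---|---|---|---|
| 20/80 | 0.023 | −48 to −6 | 0.136 | −4 to +39 |
| 30/70 | 0.0085 | −47 to −9 | 0.080 | −1 to +38 |
| 50/50 | 0.0046 | −47 to −11 | 0.066 | +1 to +37 |

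In the last cell the exact p-value and the CI disagree at the margin, which is a reason to name one of them as the main read-out.

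**How often the rule is silent.** Enumerating all outcomes gives the probability of p≤0.05 with OR<1:

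| True rates (with vs without) | 20/80 | 30/70 | 50/50 |
|---|---|---|---|
| 30% vs 60% | 66% | 77% | 83% |
| 40% vs 67% | 55% | 69% | 74% |
| 45% vs 60% | 20% | 26% | 27% |

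At 30% vs 60%, the per-stratum exact CIs overlap in 51%, 42% and 34% of those significant datasets.

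**The case against.** The case on the other side has several parts.

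- *OR>1 is the direction that matters.* In a single-arm study, other therapy threatens the osilodrostat estimate mainly by inflating response, so the rule can be read as a targeted check. But the SAP's null is non-directional, its p-value is two-sided, and the Amendment 1 rationale names no direction.
- *Nothing is lost when OR<1.* The p-value and odds ratio would still be available. That is true; what is missing is the pre-specified reading and the effect size.
- *The protocol wording may ask only for per-group CIs.* That reading is open, and protocol 8.7.12 with SAP 5.2 already provides such intervals. The difference itself is still not named, even though a reader could obtain the point value by subtraction.
- *SAP 5.3.6 is the promised elaboration, not a change.* This has some force, because the protocol defers detail to the SAP. A test with a reject rule nevertheless goes beyond detailing a descriptive difference.
- *Most of the no-testing statements exclude only formal testing.* Three of the four carry that qualifier, and SAP 5.12 concerns sample size. A stated null, a 0.05 threshold and a rejection are formal by any ordinary reading.
- *The SAP never says non-rejection means no confounding.* Correct; that is a risk of misreading, not a statement in the plan.
- *The size depends on an assumed large effect.* Correct. At 45% versus 60%, the silent outcome falls to 20–27% of datasets.
- *The strata rest on therapy received after the start of treatment.* Early discontinuers count as non-responders and may have had less time to receive other therapy. A difference on these strata inherits that problem and would not by itself establish confounding. This limits interpretation under either approach.

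**Conclusion.** The concern holds. SAP 5.3.6 sets a two-sided question and answers it in one direction only, does not name the difference that protocol 8.7.12 says will be evaluated, and uses a reject rule that both documents' no-testing statements do not allow for. SAP 5.13 does not record the departure. This follows from the text and needs no assumption.

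The size does rest on assumptions (100 patients, splits from 20/80 to 50/50, assumed rates). For true differences of 15 to 30 points in the unaddressed direction, a significant result with no stated conclusion arises in 20% to 83% of datasets. Table shells were not among the documents, so the finding concerns the SAP text. The primary estimate is not affected; the analysis is supportive, and the change should be made but is not critical.

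**What to change.** Rewrite SAP 5.3.6, for the ITT population, as follows:

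1. Report the number and proportion with mUFC ≤ULN at Week 12 in each stratum, with exact 95% CI.
2. Report the difference (yes minus no) with a two-sided 95% CI by a named method, for example Newcombe. Make it the main read-out, interpreted in both directions.
3. Remove the OR>1 condition and the reject rule.
4. Either drop the test, or keep the two-sided p-value as descriptive only and record it in SAP 5.13, with its justification, as an addition to the protocol.
5. State that p>0.05 is not read as absence of confounding.

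The strata stay as they are. The cost is one SAP paragraph, one table shell and, if the p-value is kept, one line in SAP 5.13. No new data are needed and the primary analysis does not change.
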